4.3.2. Remitters

4.3.2.1. Definition

Subjects who have a MADRS total score of ≤ 12 will be considered remitters.

4.3.2.2. Analysis Methods

The proportion of subjects who achieve remission will be summarized at each time point for each induction phase (DB and OL). The proportion of remitters during the double-blind induction phase in the esketamine dose group will be compared with the placebo group using Fisher's exact test with 90% CIs for the proportion provided by treatment group.

The cumulative distribution function of the time to sustained remission will be estimated by the Kaplan-Meier method for double-blind induction phase. Time to sustained remission will be summarized (number of sustained remitters, number of censored subjects, median, 25th and 75th percentile, if estimable) by treatment group. Sustained remission is defined as the first occurrence of remission that is maintained through the Day 28 assessment. Subjects are allowed one excursion (MADRS total score >12) on a subsequent visit prior to Day 28. Subjects who discontinue early are not considered to have sustained remission. Those subjects without sustained remission will be censored at the last visit during double-blind induction phase.

4.3.3. Time to Relapse

4.3.3.1. Definition

Time to relapse will be defined as the time between the end of the double-blind induction phase and the first documentation of a relapse event during the posttreatment phase. The relapse is defined as any of the following:

- MADRS total score ≥ 22 for 2 consecutive assessments. The date of the second MADRS assessment will be used for the date of relapse.
- Hospitalization for worsening depression or any other clinically relevant event determined per clinical judgment to be suggestive of a relapse of depressive illness such as suicide attempt, completed suicide, or hospitalization for suicide prevention. If hospitalized for any of these events, the start date of hospitalization will be used for the date of relapse. Otherwise the date of the event will be used if the subject is not hospitalized.
- In case both relapse criteria are met, the earlier date will be defined as the date of relapse for this subject.

Those subjects without relapse will be censored at the last visit (complete/withdraw) date in posttreatment phase.

4.3.3.2. Analysis Methods

The cumulative distribution function of the time to relapse will be estimated by the Kaplan-Meier method. Time to relapse will be summarized (number of relapses, number of censored subjects, median, 25th and 75th percentile, if estimable) by treatment group and the combined esketamine groups for the following groups separately.

1. In subjects who remit (MADRS total score ≤ 12) at the end of the double-blind induction phase
2. In subjects with response ($\geq 50\%$ reduction from baseline in MADRS total score) but who are not in remission at the end of the double-blind induction phase

4.3.4. Onset of Clinical Response

4.3.4.1. Definition

A subject is defined as having a clinical response if there is at least 50% improvement from baseline in the MADRS total score with onset by Day 2 that is maintained to Day 28. Subjects

are allowed one excursion (nonresponse) on Days 8, 15 or 22, however the score must show at least 25% improvement. Subjects who do not meet such criterion, or discontinue during the study before Day 28 for any reason will not be considered to have maintained clinical response and will be assigned the value of 0 (ie, no).

4.3.4.2. Analysis Methods

The proportion of subjects showing onset of clinical response by Day 2 that is maintained for the duration of the double-blind induction phase in the esketamine dose group will be compared with the placebo group using Fisher's exact test with 90% CIs for the proportion provided by treatment group. The proportion of responders with onset by Day 2 that is maintained to Day 8, Day 15, Day 22 and Day 28 will be test separately.

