Subjects assigned to esketamine 84 mg dosing will start treatment sessions with 56 mg of intranasal esketamine on Day 1 to improve tolerability. On Day 4 (Visit 3.3), the dose will be increased to 84 mg as a forced titration and remain at 84 mg for all subsequent intranasal treatment sessions. Subjects who are randomly assigned to 28 mg and 56 mg on Day 1 will remain on that dose for all subsequent intranasal treatment sessions. No adjustment to the intranasal esketamine dose is permitted during the double-blind induction phase.

Use of benzodiazepines and non-benzodiazepine sleeping medications (eg, zolpidem, eszopiclone, and zopiclone) is prohibited within 12 hours prior to the start of each intranasal treatment session.

Responders (subjects who have $\geq 50\%$ reduction from baseline in MADRS total score) at the end of the double-blind induction phase will be eligible to proceed to the posttreatment phase; those who do not (ie, nonresponders) will proceed to the 4-week follow-up phase.

If a subject withdraws before the end of the double-blind induction phase for reasons other than withdrawal of consent, the Early Withdrawal (EW) Visit should be conducted within 1 week of the date of discontinuation, followed by a 4-week follow-up phase. MADRS information will be collected during the 4 week follow-up phase. If the EW Visit occurs on the same day as a scheduled visit, the EW Visit can be performed on the same day; duplicate assessments are not required.

Given the potential for treatment-emergent transient elevation in SBP and DBP, the guidance on Blood Pressure Monitoring (see Section 6.3.1) should be followed on intranasal dosing days during the double-blind induction phase.

Posttreatment Phase

Responders who completed the double-blind induction phase will enter the 24-week posttreatment phase to evaluate durability of efficacy after cessation of add-on intranasal esketamine or placebo treatment while continuing the oral antidepressant treatment regimen, as assessed by the time to relapse and proportion of responders and remitters at each visit in this phase. All subjects who are discontinued must be treated with an oral antidepressant after completion of the study, unless it is clinically inappropriate.

Relapse is defined as any of the following:

- MADRS total score ≥ 22 for 2 consecutive assessments. The date of the second MADRS assessment will be used for the date of relapse.

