Instructions for use documents (healthcare provider versions) for intranasal study drug administration will be provided as separate documents. Details regarding study drug administration will be recorded in the source documents and the eCRF. In the event of a missed dose, ensure to contact to sponsor immediately.

Prior to the first intranasal dose on Day 1, subjects will practice spraying (into the air, not intranasally) with a demonstration intranasal device that is filled with placebo solution.

The intranasal treatment sessions (esketamine or placebo) will occur twice weekly. Subjects will self-administer the intranasal study drug (esketamine 28 mg, 56 mg, 84 mg, or placebo) at treatment sessions occurring twice a week for 4 weeks at the study-site. The first treatment session will be on Day 1. Intranasal treatment sessions should not take place on consecutive days.

To improve tolerability, subjects who will be randomly assigned to esketamine 84 mg will start at 56 mg on Day 1 and then the dose will increase to 84 mg on Day 4 as a forced titration and remain at 84 mg for all subsequent intranasal treatment sessions. Subjects who are randomly assigned to 28 mg and 56 mg dose groups will remain on that dose for all subsequent intranasal treatment sessions. No adjustment to the intranasal esketamine dose is permitted for the duration of the double-blind induction phase.

Food will be restricted for at least 2 hours before each administration of study drug. Drinking of any fluids will be restricted for at least 30 minutes before the first nasal spray.

If the subject has nasal congestion on the dosing day, an intranasal decongestant can be used to reduce congestion or the dosing day be delayed (per the permitted visit window; see the Time and Events Schedules). If an intranasal decongestant is used to reduce congestion, it cannot be used within 1 hour prior to intranasal study drug administration.

On all intranasal treatment sessions, subjects must remain at the clinical site until study procedures have been completed and the subject is ready for discharge. Subjects should be

accompanied by a responsible adult when released from the clinical study site. Subjects must not drive a car or work with machines for 24 hours after the intranasal treatment session.

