4.2.3.1. MMRM

The primary efficacy variable, change from baseline in MADRS total score at Day 28 in the double-blind induction phase, will be analyzed using a Mixed-Effect Model for Repeated

Measures (MMRM) based on observed case data. The models will include baseline MADRS total score as a covariate, and treatment, day (see [Table 1](#)), and day-by-treatment interaction as fixed effects. The between-within approximation will be used to estimate the denominator degrees of freedom. The within-subject covariance between visits will be estimated via an unstructured variance-covariance matrix. In case of convergence problems, alternative variance-covariance structures will be tried in the following order, with the first structure that converges being used in the analysis: heterogeneous Toeplitz, standard Toeplitz, and AR(1) with separate subject random effect. Comparison of each esketamine dose group with the placebo group will be performed with the appropriate contrast using a Dunnett adjustment.

[figure not shown]
The change from baseline in MADRS total score over time in the double-blind induction phase will be analyzed using the same MMRM as described above.

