5.1. Adverse Events

The Medical Dictionary for Regulatory Activities (MedDRA) (version 20.0 or above) will be used to classify adverse events (AEs) by system organ class and preferred term. Treatment-emergent adverse events (TEAEs) that occurred in each analysis phase (DB induction, DB follow-up, PT, OL induction, OL follow-up) will be summarized by system organ class and preferred term.

The number (%) of subjects with TEAEs, serious TEAEs (SAEs), and TEAEs that led to study drug discontinuation, dose reduction will be summarized by system organ class and preferred term. TEAEs will be summarized by onset time (4 week intervals). Data listings will be generated for deaths, other SAEs, and discontinuations due to AEs.

A TEAE is an event that is new in onset or increased in severity following treatment initiation. An event that starts prior to, and ends after the initiation of study medication will be considered treatment-emergent only if the severity increases after the start of medication.

Treatment-emergent adverse events (TEAEs) are defined as follows for each analysis phase:

- TEAEs in DB induction phase:
 - a. If AE onset time is not missing: DB start date/time \leq AE onset date and time \leq DB end date
 - b. If AE onset time is missing: DB start date \leq AE onset date \leq DB end date
- TEAEs in OL induction phase:
 - a. If AE onset time is not missing: OL start date/time \leq AE onset date and time \leq OL end date
 - b. If AE onset time is missing: OL start date \leq AE onset date \leq OL end date
- AEs in DB follow-up phase: DB FU start date \leq AE onset date \leq DB FU end date
- AEs in OL follow-up phase: OL FU start date \leq AE onset date \leq OL FU end date

- For the AEs that have both day and month missing, treatment-emergent flag is assigned based on the rules presented in Section 2.6.

In addition, TEAEs will be summarized by severity and relationship to study medication using the preferred term. For the summaries of TEAEs by severity/relationship to study medication, the observation with the most severe occurrence/closest relationship to study medication will be chosen if there is more than one incident of an AE reported during the analysis phase by the subject.

Adverse Events of Special Interest

Clinically relevant TEAEs of special interest will be examined separately grouped in the following categories:

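### At Day 2 the 84 mg arm has received only 56 mg, yet the SAP reports its Day 1 and Day 2 results as 84 mg and tests it apart from the identically treated 56 mg arm

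*SAP*

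**What the plan says.** Protocol 3.1 sets the doses: "Subjects assigned to esketamine 84 mg dosing will start treatment sessions with 56 mg of intranasal esketamine on Day 1 to improve tolerability". At the Day 4 visit, "the dose will be increased to 84 mg as a forced titration and remain at 84 mg for all subsequent intranasal treatment sessions". For the other active arms, "Subjects who are randomly assigned to 28 mg and 56 mg on Day 1 will remain on that dose for all subsequent intranasal treatment sessions". Protocol 6.3 repeats that "subjects who will be randomly assigned to esketamine 84 mg will start at 56 mg on Day 1". Time and Events Schedule 1 gives the Day 4 visit a window of plus or minus 1 day, so the first 84 mg dose falls between Day 3 and Day 5. The same schedule places a remote MADRS interview on Day 2.

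The SAP works by assigned arm:

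- Table 1 (SAP 2.3) makes Day 2 a MADRS analysis visit of its own.
- SAP 4.2.3.1 applies the primary model to "The change from baseline in MADRS total score over time in the double-blind induction phase".
- SAP 4.3.1.2 summarises responders at each time point and compares the double-blind proportions with placebo by Fisher's exact test.
- SAP 4.3.4.1 defines onset of clinical response as at least 50% MADRS improvement "with onset by Day 2 that is maintained to Day 28". SAP 4.3.4.2 tests against placebo the proportion showing "onset of clinical response by Day 2 that is maintained for the duration of the double-blind induction phase in the esketamine dose group", and also tests maintenance to Days 8, 15 and 22.
- SAP 5.3 and 5.5.2 to 5.5.4 present vital signs, CADSS, BPRS+ and MOAA/S by dosing day, Day 1 included.
- SAP 5.1 says "TEAEs will be summarized by onset time (4 week intervals".

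The design summary in SAP 1.2 describes the open-label titration but not the double-blind one. SAP 3.3 plans summaries of modal, mean and final intranasal dose for the open-label phase only.

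**The concern.** Dose response and onset of response are both secondary objectives of this dose-finding study. At Day 2 the plan gives two sets of results, one labelled 56 mg and one labelled 84 mg, for what is a single treatment. Any gap between them is chance, but the labels invite a reader to see a dose effect.

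The safety labelling may matter more. Protocol 1.2 singles out the safety of 84 mg in Japanese subjects with TRD for careful assessment. Protocol 3.2.4 reports that dissociative effects were greatest at first on 84 mg and eased with repeated dosing. An unannotated Day 1 figure for the 84 mg arm would be taken as tolerability of a first dose of 84 mg, which no subject in the double-blind phase receives.

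A 4-week onset interval covers the whole 4-week phase. It cannot show whether an adverse event began before or after the step to 84 mg.

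**Working it through.** **The plan's own figure.** Inputs from Protocol 11.2: differences of 4, 4.5 and 5 points, SD 10, one-sided 0.05, 12.5% drop-out. Evaluable numbers of 63 placebo and 32 per dose give 63/0.875 = 72 and 32/0.875 = 36.6, rounded up to 37. The total is 72 + 3 × 37 = 183, as stated. Dunnett power for at least one dose is 79.4% (normal) or 78.7% (t), against a stated 80%. The Week 4 design reproduces, and nothing below alters it.

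**Exposure by assessment.**

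| Assessment | 56 mg arm has received | 84 mg arm has received |
|---|---|---|
| Day 1 postdose safety | 56 mg | 56 mg |
| Day 2 MADRS | 56 mg | 56 mg |
| Day 8 MADRS (predose) | 56 + 56 mg | 56 + 84 mg |
| Day 28 MADRS | 8 sessions at 56 mg | 1 at 56 mg, 7 at 84 mg |

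The arms are the same treatment up to the second session and differ from then on.

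**Two tests of one treatment at Day 2.** The documents give no Day 2 SD or effect, so SD 10 and differences of 3 to 5 points are assumptions. Group sizes are 72 and 37.

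- SE of one arm against placebo: 10 × √(1/72 + 1/37) = 2.02 points.
- Correlation of the two tests, through the shared placebo group: 37/(37 + 72) = 0.34.
- P(exactly one significant) = 2 × [P(at least one) − P(a given one)].

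| True difference | A given arm significant | At least one | Exactly one |
|---|---|---|---|
| 3 | 43.6% | 62.8% | 38% |
| 4 | 63.0% | 81.3% | 37% |
| 4.5 | 71.9% | 88.0% | 32% |
| 5 | 79.6% | 92.8% | 26% |

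With no true effect, at least one of the two is nominally significant 9.2% of the time. The SE of the difference between the two arms is 10 × √(2/37) = 2.32 points, so chance alone separates them by 2 points or more 39% of the time.

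**Pooling at Day 2.** With 74 against 72, the SE in SD units is √(1/72 + 1/74) = 0.1655, against √(1/72 + 1/37) = 0.2023 for one arm. The ratio is 0.818, so the SE falls by 18% and the variance by 33% (0.818² = 0.67). Nominal one-sided power rises from 44% to 57% at 3 points, 63% to 78% at 4, 72% to 86% at 4.5 and 80% to 92% at 5.

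For response at Day 2 alone, exact one-sided Fisher power at assumed rates rises from 42% to 55% (5% placebo, 15% active), from 85% to 96% (5%, 25%) and from 74% to 89% (10%, 30%). These figures do not apply to the sustained-onset endpoint.

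**The case against.** The strongest reply is that the protocol openly defines the 84 mg arm as a titrated regimen. Comparing randomized arms is then a valid comparison of regimens at every visit. That stands. It also stands that all tests other than the Day 28 Dunnett comparison are nominal (SAP 4.1.1), that MCP-Mod uses Day 28 estimates only (SAP 4.2.3.3), that PK is sampled on Days 4 and 25 (SAP 6.1.1), and that no 56 mg versus 84 mg test is planned at Day 2. A reader might infer a type I error problem or a fault in the primary analysis; the documents support neither.

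A reader might also infer that the onset-of-response result for the 84 mg arm is simply a 56 mg result. It is not. SAP 4.3.4.1 and 4.3.4.2 contain no Day-2-only test. Every version of the endpoint requires response to be maintained to Day 8 or later, after the step to 84 mg.

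Nor are Day 1 safety data mixed with 84 mg data. Vital signs and the scales have separate Day 1 and Day 4 analysis windows, and a by-subject dosing listing is planned. What is missing is the label. The 4-week adverse event table was not stated to be a tool for separating doses, but it is the only onset-time summary planned.

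Finally, it would be too strong to say that half of the Day 2 information goes unused. Both arms are in the model, and the gain from pooling is a 33% cut in the variance of the contrast.

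**Conclusion.** The point holds as one of labelling and interpretation. The Day 2 MMRM contrast, the Day 2 responder comparison and the Day 1 safety outputs for the 84 mg arm each reflect one 56 mg dose. The SAP neither says so nor pools the two identically treated arms. Its size, under an assumed Day 2 SD of 10 with 72 and 37 subjects, is a 26% to 38% chance that exactly one of two identical arms is nominally significant when the true difference is 3 to 5 points. The exposure facts need no assumption. The percentages depend on the assumed SD and effects, and on reading SAP 4.2.3.1 and 4.3.1.2 as giving comparisons at each analysis visit in Table 1. The sample size and Week 4 power do not change.

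**What to change.** 1. State the double-blind titration in SAP 1.2, and label or footnote the 84 mg arm's Day 1 and Day 2 outputs with the dose received by then, 56 mg.
2. Prespecify a supportive Day 2 analysis of the 56 mg and 84 mg arms pooled against placebo (74 versus 72), for MADRS change and for response at Day 2. Keep the randomized-arm analyses, and keep the onset endpoint of SAP 4.3.4 by arm, because the arms differ from the second session. SAP 4.3.3.2 already combines esketamine groups for time to relapse.
3. In the double-blind phase, replace the 4-week adverse event onset interval with onset before, versus on or after, each subject's actual second dosing session, using the same rule in all arms. In the 84 mg arm this is the first 84 mg dose. A fixed split at Day 4 would misclassify events in subjects dosed on Day 3 or Day 5, and weekly intervals would mix both doses in week 1.

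The cost is SAP wording, one extra contrast and one label. No new data are needed and no change to dosing is implied.

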4.3.5. CGI-S

4.3.5.1. Definition

The Clinical Global Impression of Severity (CGI-S) provides an overall clinician-determined summary measure of the severity of the subject's illness that takes into account all available information, including knowledge of the subject's history, psychosocial circumstances, symptoms, behavior, and the impact of the symptoms on the subject's ability to function. The CGI-S evaluates the severity of psychopathology on a scale of 0 to 7. Considering total clinical experience, a subject is assessed on severity of mental illness at the time of rating according to: 0=not assessed; 1=normal (not at all ill); 2=borderline mentally ill; 3=mildly ill; 4=moderately ill; 5=markedly ill; 6=severely ill; 7=among the most extremely ill patients. The CGI-S permits a global evaluation of the subject's condition at a given time.

4.3.5.2. Analysis Methods

Descriptive statistics of actual values and changes from baseline by treatment group will be provided. Frequency distributions by treatment group will be provided at each time point for each analysis phase (DB induction, DB follow-up, PT, OL induction and OL follow-up).

The ranks of the change from baseline for CGI-S in the double-blind induction phase will be analyzed at each time point based on observed case using the same MMRM as described in Section 4.2.3.1 for primary efficacy endpoint, with the covariate "baseline MADRS total score" changed to "baseline CGI-S".

4.3.6. Sheehan Disability Scale (SDS)

4.3.6.1. Definition

The SDS is a subject-reported outcome measure and is a 5-item questionnaire which has been widely used and accepted for assessment of functional impairment and associated disability. The first three items assess disruption of (1) work/school, (2) social life, and (3) family life/home responsibilities using a 0-10 rating scale. The score for the first three items are summed to create a total score of 0-30 where a higher score indicates greater impairment. It also has one item on days lost from school or work and one item on days when underproductive. The recall period for

this study is 7 days. Scores ≤ 4 for each item and ≤ 12 for the total score are considered response. Scores ≤ 2 for each item and ≤ 6 for the total score are considered remission. If any of the first three items are missing, the total score will be set to missing as well as response and remission status.

4.3.6.2. Analysis Methods

Descriptive statistics of actual values and changes from baseline by treatment group will be provided at each time point for DB induction and PT phases. The total score as well as the individual item scores will be summarized separately. Graphical presentations will also be provided. In addition, the proportion of subjects who achieve response and remission will be summarized at each time point during the double-blind induction phase.

The change from baseline in SDS total score at Day 28 in the double-blind induction phase will be analyzed using the same MMRM as described in Section 4.2.3.1 for primary efficacy endpoint, with the covariate “baseline MADRS total score” changed to “baseline SDS total score”.

4.3.7. GAD-7

4.3.7.1. Definition

The GAD-7 (Generalized Anxiety Disorder - 7 Items) is a brief and validated 7-item self-report assessment of overall anxiety.^{10,11} Subjects respond to each item using a 4-point scale with response categories of 0=not at all, 1=several days, 2=more than half the days, and 3=nearly every day. Item responses are summed to yield a total score with a range of 0 to 21, where higher scores indicate more anxiety. The recall period is 2 weeks. The severity of the GAD-7 is categorized as follows: None (0-4), Mild (5-9), Moderate (10-14) and Severe (15-21).

